# Appendix B. Sample Serious Adverse Event Form or eSerious Event Contingency Form

AMGEN	Ele	ectronic Se	erious Ac	dvers	e E	vent	C	ontin	ge	ncy	Rep	ort Fo	rm
Study # 20170533 AMG 562		For Restricted Use											
Reason for reporting thi													
The Clinical Trial Databa													
□ Is not available due to i			ite										
Is not yet available for		-											
Has been closed for this study      <-For completion by COM prior to providing to sites: SELECT OR TYPE IN A FAX#>>													
1. SITE INFORMATION	npreuo	n by com prio	r to proviain	ig to si	es: s	ELEC	.10	RITE		AFA	X#22		
Site Number		Investigator							0	Country			
Reporte			Phone Number					Eavl	lumber				
Reporte			()					(		)			
2. SUBJECT INFORMATION	N												
Subject ID Number		Age at event onset			Sex			Race		lf appli date	cable, p	rovide End of S	audy
						ur LiN	n						
If this is a follow-up to an event rep		he EDC system (eg,	Rave), provide th	e adverse	event t	erm:						i	ind
start date: Day Month 3. SERIOUS ADVERSE EVE													
Provide the date the Investigator be	came aw	are of this informatio	n: Day Mo		/ear								
Serious Adverse Event diagnosis or s If diagnosis is unknown, enter signs / sy	mptoms an			Check only if	~	ifserious, enter	is th	ere a reasor		ssibility the		nt of Event	Check only If event is related to
provide diagnosis, when known, in a follo List one event per line. If event is fatal			Date Ended	occurred	serious?	Serious Criteria	IP or a	may h n Amgen de		n caused b ed to admir		IP? Reserved	study procedure
cause of eeath. Entry of "death" is not . as this is an outcome.				before first dose	event se	code (see						Fatal Unknown	eg, biops
as this is an outcome.		Day Month Year	Day Month Year	of IP	ls eve	codes below)		3912 4 2/	daine-	

	<p m<="" td="">nib-		
	nib-	
		bay month real	bay month rear		_	Delowy		Yes- No-					 
					Yes No								
					Yes No								
					Yes				$\vdash$				
Serious 01 Fatal			prolonged hospita		05 Congenital anomaly / birth defect								
Criteria: 02 Immediately life-thr			t or significant disa									ant serious ev	
4. Was subject hospitalized	d or was ate Admit		on proionged	aue this	even	π? ⊔N	10 L	Date D			mprete	all of Sectio	ni <del>4</del>
Day	Month	Year					D		onth	Year	r		
5 Was IP/drug under study	admin	istorod/takon ari	ior to this our	nt2 ⊡N		or Hur	e ele	250.00-	unlete	all of C	action (	5	
5. Was IP/drug under study	aumin	istereu/taken pri	ion to this eve			es ITye ime of Ev		ase com	ipiete	Action	Taken		
		Date of Initial Dose	Date of	Dose	Do	se F	loute	Frequ	ency	with P 01 Still			
										Adminis 02 Perm	tered	Lot # and	Serial #
ID/Among Davis		Davis Marcilla M								disconti 03 With	nued		
IP/Amgen Device:		Day Month Yea	a Day Month	n Year	+					05 WID	neiu	Lot #	
												Unknown Serial #	
												Unavailabi	e/
AMG 562 S open label												Unknown Lot#	
												Unknown Serial #	
< <ip device="">> □ blinded □ op</ip>	en label											Unavailab Unknown	e/
EORM-056006								larsion 7	0	Effective	Date	1 February	2016

Page 1 of 3

AMGEN Study # 20170533 AMG 562	Electronic Se	ctronic Serious Adverse Event Contingency Report Forr For Restricted Use						
	Site Number	Subject ID Number						

	╾┼╾┼╾┼╾┼╾┼╸		30	e nump	er				30	Subject ib Number									
6. CON	6. CONCOMITANT MEDICATIONS (eg, chemotherapy) Any Medications? ON O Yes If yes, please complete:																		
M	edication Name	e(s)		tDate with Year	r De		p Date onth Y	fear	Co-si Nov	uspect Yes√	Con No-/	tinuing Yes⁄	D	ose	Ro	ute	Freq.	Treat No-	tment Med Yes⁄
7. REL	EVANT MEDI	CAL HIST	ORY (in	clude	dates.	alle	ergies	s an	d any	relev	ant p	prior th	erap	(v)					
							-												
8. REL	EVANT LABO	RATORY	VALUE	S (incl	ude b	asel	line v	alu	es) A	ny Rele	vant l	Laborat	ory va	ues? 🗆	No D	Yes	lf yes, pl	ease co	mplete:
	Test			· ·		Τ		Τ		Í			-						
Date	Unit					1									+				
Day	Month Year					+		+		-					+		_		
9. OTH	IER RELEVAN	IT TESTS	(diagno	stics a	and pr	oce	durea	s)		Any O	ther F	Relevan	t tests	? 🗆 N	lo 🗆	Yes	lf yes, pl	ease co	mplete:
Dey	Date Month Year		A	ddition	al Tes	ts							Resu	lts				Unit	s

FORM-056006

Page 2 of 3

Version 7.0 Effective Date: 1 February 2016

AMGEN Study # 20170533	Electronic Serious Adverse Event Contingency Report Form							
AMG 562	For Restricted Use							
	Site Number	Subje	t ID Number					

 
CASE DESCRIPTION (P event in section 3, where relat
 
			section 3) Pro	vide additio	nai pages ir ne	cessary. For each		
Signature of Investigator or Desig	nee -		Title			Date		
I confirm by signing this report that t	he information on this form, in	cluding seriousness and						
causality assessments, is being provi a Qualified Medical Person authorize	ded to Amgen by the investiga	tor for this study, or by						

Approved

FORM-056006

Page 3 of 3

Version 7.0 Effective Date: 1 February 2016

# Appendix C. Pregnancy and Lactation Notification Worksheets

AMCEN ® Pregnancy Notification Worksheet								
Fa	Completed For	n to the Country-r	espective S	afety Fax Line				
4. Com Administration In	US: [contact]	_					
1. Case Administrative Inf Protocol/Study Number: 2017053								
Study Design: Interventional	Observational	(If Observational:	Prospective	Retrospective)				
2. Contact Information								
Investigator Name Phone ()				Site #				
				Email				
Institution Address								
7441633								
3. Subject Information								
Subject ID #	Subject Gen	der: 🗌 Female 🗌	Male Su	bject DOB: mm/dd/yyyy				
4. Amgen Product Exposu	IFO.							
4. Amgen Froduct Expost	lle							
Amgen Product	Dose at time of conception	Frequency	Route	Start Date				
				mm -//dd -//yyyy				
Was the Amgen product (or st	udy drug) discontinu	ed? 🗌 Yes 📃 N	0					
If yes, provide product (or	study drug) stop da	te: mm 🔄/dd	_ /yyyy					
Did the subject withdraw from	the study? 🔲 Yes	No						
5. Pregnancy Information								
Pregnant female's LMP mm		yyyy 🗌 Unl						
	Estimated date of delivery mm/ / dd/ yyyy Unknown N/A							
Has the pregnant female already d				-				
If yes, provide date of deliver								
Was the infant healthy?								
If any Adverse Event was experien	ced by the infant, pr	ovide brief details:						

Form Completed by:	
Print Name:	Title:
Signature:	Date:

Effective Date: March 27, 2011

Page 1 of 1

**AMGEN**®

AMGEN	Lactation	Notification	Worksheet
	Lactation	Notification	Worksheet

Fax Completed Form to the		ve Safety Fax Line		er fax number
1. Case Administrative Inf				
Protocol/Study Number: 201705	33			
Study Design: 🗹 Interventional	Observational	(If Observational:	Prospective	Retrospective)
2. Contact Information				
Investigator Name				Site #
Phone ()	Fax (	)		Email
Institution				
Address				
3. Subject Information				
Subject ID #	Subject Date	of Birth: mm	/dd/y	yyy
4. Amgen Product Exposu	ire			
Amgen Product	Dose at time of breast feeding	Frequency	Route	Start Date
				mm/dd/yyyy
Was the Amgen product (or st	udv drug) discontinu	ed? Yes N	0	
If yes, provide product (or				
Did the subject withdraw from				-
		—		
5. Breast Feeding Informa	tion			
			le actively tak	ing an Amgen product? 🗌 Yes 📃 No
If No, provide stop date: m				
Infant date of birth: mm/o				
Infant gender: Female				
Is the infant healthy? Yes	No Unknown	N/A		
If any Adverse Event was experienced by the mother or the infant, provide brief details:				

Form Completed by:	
Print Name:	Title:
Signature:	Date:

Effective Date: 03 April 2012, version 2.

Page 1 of 1

# Appendix D. Response Assessment per the Lugano Classification

- 5- point scale (Deauville)
- 1. no uptake above background;
- 2. uptake  $\leq$  mediastinum;
- 3. uptake > mediastinum but  $\leq$  liver;
- 4. uptake moderately > liver;
- 5. uptake markedly higher than liver and/or new lesions;
- X. new areas of uptake unlikely to be related to lymphoma.

Response	Compete Response	Partial Response	Stable Disease	Progressive Disease
PET/CT Response	Complete Metabolic Response	Partial Metabolic Response	No Metabolic Response	Progressive Metabolic Disease
Target Masses	Score 1, 2, or 3 with or without a residual mass	Score 4 or 5 reduced uptake compared with baseline residual mass(es) of any size	Score 4 or 5 no significant change in FDG uptake from baseline	Score 4 or 5 with an increase in intensity of uptake from baseline and/or new FDG-avid foci consistent with lymphoma
New Lesions	None	None	None	New FDG-avid foci consistent with lymphoma rather than another etiology
Bone Marrow	No FDG avid focal lesions	Residual uptake higher than uptake in normal marrow but reduced compared with baseline	No change from baseline	New or recurrent FDG-avid foci

# Appendix E. Medications That May Cause QTc Prolongation

A list of medications known to cause QTc interval prolongation is available at the following link: https://crediblemeds.org/index.php/login/dlcheck

If a participant in this study does not have access to the internet, they can contact the institution investigational pharmacy or contact their study physician to obtain a list.

Table 19 presents a list of drugs that may prolong QTc. This is not an inclusive list of drugs and is provided for guidance only. The participant is encouraged to follow the list in this link above for the most up-to-date information. Use of these drugs should be discussed with the Amgen Medical Monitor. Washout period is based on roughly 5 half-lives and rounded to a convenient interval. This list includes (but is not limited to) the following:

Compounds	Compound Half-Life	Possible Washout Period – Hours	Possible Washout Period - Days
Alfuzosin	~10 hours		7
Amantadine	17 ± 4 hours (10-25)		4
Amiodarone (cordarone)	58 days (15-142) 36 days (active metabolite)		180
Amitriptyline*	> 24 hours, wide interpatient variability		
Arsenic trioxide	Not characterized		
Azithromycin	40 hours		
Bepridil	42 hours (26-64)		10
Chloral hydrate	Readily converted to trichloroethanol (active metabolite $T_{\frac{1}{2}}$ = 7-10 hours)	48	
Chloroquine	Prolonged (days to weeks)		
Chlorpromazine	30 ± 7 hours		
Clarithromycin	Non-linear PK 3-4 hr (250 mg Q12) 5-7 hr (500 mg Q12)	36	
Chloroquine	6 to 60 days; mean 20 days		
Desipramine*	> 24 hours, wide interpatient variability		
Disopyramide	6.7 hr (4-10)	36	
Dofetilide	10 hours	48	
Dolasetron	8.1 hours		
Domperidone	7-8 hours	48	
Doxepin*	> 24 hours, wide interpatient variability		
Droperidol	2.2 hours	10	
Erythromycin	*Each salt form has different Half-Life*		

Footnotes defined on last page of this table

Page 1 of 3

Page	148	of	158
------	-----	----	-----

Compounds	Compound Half-Life	Possible Washout Period – Hours	Possible Washout Period - Days
Felbamate	20-23 hours		5
Flecainide	20 hours (12-27)		5
Foscarnet	87.5 ± 41.8 hours *distribution and release from bone*		20
Fosphenytoin	12-29 hours		6
Gatifloxacin	7-14 hours	48	
Gemifloxacin	7 hours	48	
Grepafloxacin	16 hours		3
Halofantrine	6-10 days (variable among individual)		45
Haloperidol	18 ± 5 hours		5
Ibutilide	6 hours (2-12) *variable among subject*	36	
Imipramine*	> 24 hours, wide interpatient variability		
Indapamide	14 hours (biphasic elimination)		3
Isradipine	8 hours (multiple metabolites)	48	
Levofloxacin	6-8 hours	48	
Levomethadyl	Multiple compartment PK with active metabolite		20
	2.6 days for LAAM, 2 day for nor-LAAM, 4 day for dinor-LAAM		
Lithium	24 hours (10-50)		7
Mesoridazine	24-48 hours (animal study)		10
Methadone	15-30 hours		7
Moexipril/HCTZ	2-9 hour (include active metabolite) for moexipril; 5.6-14.8 hours for HCTZ	48	
Moxifloxacin	12 ± 1.3 hours	72	
Naratriptan	6 hours	36	
Nicardipine	~ 2 hour post IV infusion	12	
Nortriptyline*	> 24 hours, wide interpatient variability		
Octreotide	1.7 hours	12	
Ofloxacin	5 to 7.5 hours		2
Ondansetron	4 hours (IV/IM); 3 hours (PO)		1 to 3
Pentamidine	6.4 ± 1.3 hours	36	
Pimozide	55 hours		10
Procainamide	3-4 hours for PA and NAPA (active metabolite)	24	
Protriptyline*	> 24 hours, wide interpatient variability		
Quetiapine	6 hours	36	
Quinidine	6-8 hours in adult; 3-4 hours in children	36	

# Table 19. Medications That May Cause QTc Prolongation

Footnotes defined on last page of this table

Page 2 of 3

-	•	
Compound Half-Life	Possible Washout Period – Hours	Possible Washout Period - Days
4-5 hours		
3-20 hours (extensive to poor metabolizer)		4
9-hydroxyrisperidone (active metabolite) T½ = 21-30 hours (extensive to poor metabolizer)		
5.5 hours (only 1 datum)	36	
12 hours	72	
20 hours (16-30)		4
2.5 hours	12	
~34 hours in healthy; ~19 hours in kidney transplant		7
5-7 days (biphasic)		30
2-3 hours	24	
20-40 hours (phenothiazines)		7
2.5 hours	12	
4 to 5 hours		
5 ± 2 hours for parent comp.	60	
11 $\pm$ 2 hours for OVD (active metabolite)		
6 hours; dose dependent		
7 hours	36	
2.8-3.7 hours (higher in female)	18	
	
 
4-5 hours
 
3-20 hours (extensive to poor metabolizer)
 
9-hydroxyrisperidone (active metabolite)
 
T/2 = 21-30 hours (extensive to poor metabolizer)
 
5.5 hours (only 1 datum)
 
12 hours
 
20 hours (16-30)
 
2.5 hours
 
~34 hours in healthy; ~19 hours in kidney transplant
 
5-7 days (biphasic)
 
2-3 hours
 
20-40 hours (phenothiazines)
 
2.5 hours
 
4 to 5 hours
 
5 ± 2 hours for parent comp.
 
11 ± 2 hours for OVD (active metabolite)
 
6 hours; dose dependent
 
7 hours
 
	Compound Half-LifeWashout Period – Hours4-5 hours3-20 hours (extensive to poor metabolizer)3-20 hours (extensive to poor metabolizer)9-hydroxyrisperidone (active metabolite) Ty2 = 21-30 hours (extensive to poor metabolizer)3612 hours (only 1 datum)3612 hours7220 hours (16-30)722.5 hours12~34 hours in healthy; ~19 hours in kidney transplant245-7 days (biphasic)242-3 hours2420-40 hours (phenothiazines)252.5 hours124 to 5 hours6011 ± 2 hours for OVD (active metabolite) 6 hours; dose dependent607 hours36

#### Table 19. Medications That May Cause QTc Prolongation

Page 3 of 3

\* Weakly associated with Torsades de pointes and/or QT prolongation but that are unlikely to be a risk for Torsades de pointes when used in usual recommended dosages and in patients without other risk factors (eg, concomitant QT prolonged drugs, bradycardia, electrolyte disturbances, congenital long QT syndrome, concomitant drugs that inhibit metabolism).

Sources: Drug Facts and Comparison 2006, 2005; Physician's Desk Reference, 2002; and Goodman & Gilman's the Pharmacological Basis of Therapeutics, 1996.

#### Appendix F. Performance Status According to Eastern Cooperative Oncology Group (ECOG) Scale

ECOG Performance Status Scale			
Grade	Descriptions		
0	Fully active, able to carry on all pre-disease performance without restriction.		
1	Restricted in physically strenuous activity, but ambulatory and able to carry out work of a light or sedentary nature (eg light housework, office work).		
2	Ambulatory and capable of all self-care, but unable to carry out any work activities. Up and about more than 50% of waking hours.		
3	Capable of only limited self-care, confined to bed or chair more than 50% of waking hours.		
4	Completely disabled. Cannot carry on any self-care. Totally confined to bed or chair.		
5	Dead.		

Source: Oken et al, 1982

Alfentanil
Astemizole*
Cisapride*
Cyclosporine
Diergotamine
Ergotamine
Fentanyl
Pimozide
Quinidine
Sirolimus
Tacrolimus

Appendix G. Examples of CYP450 Substrates With Narrow Therapeutic Range

Terfenadine\*

\*Not available in the US

Approved

## Appendix H. Extended Neurological Examination

Abnormalities of the following should be recorded: level of consciousness, orientation, vision, cranial nerves and brain stem functions, pyramidal and extra pyramidal motory system, reflexes, muscle tone and trophic findings, coordination, sensory system, neuropsychological findings (eg, speech, cognition and emotion). Neurological examiniations will include a wrting test to detect cerebral signs. For the writing tests, patients will be asked to write down the current date and time as well as an arbitrary sentence (this should be the same sentence throughout the study).

		1		
Study Day	Infusion Length (hr)	PK Draw Timepoint since Start of Infusion	Suggested PK Draw Windows	
		Pre-Dose		
4		(EOI)		
1		6 hours	± 15 mins	
		12 hours		
2		24 hours		
3		48 hours	± 1 hour	
4		72 hours		
0		Pre-Dose		
8		(EOI)	± 15 mins	
45		Pre-Dose		
15		(EOI)	± 15 mins	
		Pre-Dose		
	(EOI)	(EOI)		
22		6 hour	± 15 mins	
		12 hour		
23		24 hours		
24		48 hours	± 1 hour	
25		72 hours		

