#### 2.4.1 Dose Selection Rationale

The planned doses of AMG 562 in this study are 0.1, 0.3,

AMG 562 human PK profiles and exposures were predicted using a 2-compartment model with parallel linear and non-linear elimination that accounts for observed non-linearity in AMG 562 PK following repeat-dose administration in cynomolgus monkeys. Human PK parameters were scaled using allometry from estimated PK parameters in cynomolgus monkey studies described in Section 2.2.2. Based on predicted AMG 562 PK, a starting dose of 0.1 µg following a clinical IV infusion (1 hour) is predicted to acheive maximum serum concentrations approximating the MABEL (in vitro concentration required for half-maximal effect [EC50] of AMG 562-mediated autologous B cell depletion, 35.7 pg/mL). The use of the EC50 as the MABEL and basis for the FIH starting dose is supported by the previous and safe implementation of this strategy to identify the maximum recommended starting doses of previous bi-specific CD3-targeting molecules in clinical development while minimizing the number of dose escalations necessary to establish a maximum tolerated dose (Saber et al., 2017).

Additionally, relative to human exposure predictions at the starting dose, mean AUC168hr and Cmax exposures achieved at the highest non-severely toxic dose (HNSTD) of the flat-dose regimen of 5  $\mu$ g/kg in the 33-day toxicology study in cynomolgus monkeys were approximately 1800-fold and 320-fold greater than human AUC168hr and Cmax exposures predicted at the 0.1  $\mu$ g starting dose, respectively, after correction for a 17-fold potency difference in human and cynomolgus monkey effector cells. Of note, relative to the step-dose regimen of 5  $\mu$ g/kg followed by a step up to 50  $\mu$ g/kg (5/50  $\mu$ g/kg) also

evaluated in the 33-day toxicology study,  $AUC_{168hr}$  and  $C_{max}$  exposures were approximately 20000-fold and 3400-fold greater than human exposure predictions, after a 17-fold potency correction.

Subsequent planned escalations in AMG 562 dose up to  $\mu$ g are shown in Table 5. At the highest planned clinical dose of  $\mu$ g, the ratio of mean AUC168hr and Cmax exposures achieved at the 5 µg/kg HNSTD in the 33-day toxicology study in cynomolgus monkeys and predicted human AUC168hr and Cmax exposures were approximately

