f Serum pregnancy test required at screening. For later time points, urine pregnancy test is allowed. In case of a positive result, serum pregnancy test should be repeated. Pregnancy tests will be performed for all females unless surgically sterile or ≥ 2 years postmenopausal.

 Ferritin assessment to be performed at onset of CRS, and daily until values are back to baseline/event is resolved.

h Predose anti-AMG 562 antibody sample in every 2nd cycle after cycle 1 (C1D1, C1D15, C3D1, C5D1, ..).

o PET/CT will be performed at screening, week 5, week 15, week 25 and and at end of treatment if end of treatment is at week 35 or beyond. Clinical tumor assessments will be performed at screening, week 5, week 15, week 25 and at end of treatment if end of treatment is at week 35 or beyond. Every attempt should be made to complete PET and CT within 3 days of each other, particularly during treatment. If subject discontinues study treatment for any reason, including toxicity or clinical evidence of disease progression, PET/CT should be conducted 14 (+ 3) days following the last dose of AMG 562.

p In case of seizure of any grade perform brain MRI and cerebro spinal fluid (CSF) analysis, if there are no contraindications.

a As indicated in Section 7.3.10, hematology and chemistry panels include differential cell counts and comprehensive metabolic profile, as well as serum uric acid and phosphorous levels, and liver function tests. Coagulation panel includes prothrombin time (PT), partial thromboplastin time (PTT), fibrinogen and D-dimer r PK samples should be collected at the exact nominal time point specified; all times are relative to the start of infusion. The **secified** hour sample is the same as the end of infusion and should be collected as close as possible to the end of infusion of AMG 562. If unable to collect a PK sample at the specified nominal time point, then collect the sample as close as possible and record the actual collection time. The exact date and time of IP administration and PK sample collection should be documented. Additional PK samples may be collected per the discretion of the PI as clinically indicated.

s MRI of the brain to be performed at screening. To be repeated during treatment in case of seizure

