# 7.2 General Study Procedures

A signed and dated IRB/IEC approved informed consent form (ICF) must be obtained prior to performing any study specific procedures, including discontinuing standard therapy for observing study specific washout periods.

Subjects will be seen in the clinic for study evaluations. When ECGs, vital signs, and invasive procedures like blood or BM sampling occur on the same visit, ECGs and vital signs should be collected prior to performing any invasive procedures.

Blood samples for biomarker and PK assessments should be drawn from a peripheral vein and not from a central venous catheter. The study specific lab manual will provide additional detail on lab sampling and handling requirements.

Study procedures should be performed and samples obtained at the time points stipulated in the Schedules of Assessments (Table 8 through Table 11).

Acceptable deviation windows for study procedures are listed below:

- ECGs, etc., safety labs, vital signs (incl. pulse oximetry):
  - ± 15 minute window if collected within the first 24 hours (excluding the 24 hour sample) after the start of an infusion
    - ± 1 hour window if collected 24 or 48 hours after the start of an infusion
- PK blood draws see Appendix I.

Starting with Day 4 post infusion, assessments should be performed on the indicated study day prior to infusion.

Acceptable deviation windows for study visits are listed below:

- Visits during treatment-free interval, if applicable: ± 1 day
- SFU: +7 days
- LTFU: ± 7 days for on-site visits, ± 2 weeks for remote survival follow-up

Furthermore, start of a treatment can be delayed for administrative/logistical reasons for up to 7 days to allow for appropriate scheduling after discussion with and final approval by sponsor.

The DLRT may recommend a  $\pm$  1 day window for infusions following the day 1 infusion.

The DLRT may also recommend to reduce the number of infusions for a dose cohort. If no infusion was administered on Day 8, 15, and/or 22, all assessments that occur > 1 time on the respective day only have to be performed once, at any time during that day. Also, the following assessments scheduled for 24 hours, 48 hours, and 3 days post infusion would not be mandatory in that case: physical examination, vital signs,

ECG, hematology, chemistry, coagulation, urinalysis, PK and the following

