## 3. Study Overview

## 3.1 Study Design

This is a multicenter, Phase 1, first-in-human (FIH), non-randomized, open-label study in adult subjects with relapsed / refractory DLBCL, MCL, or FL. AMG 562 will be administered weekly as short term IV infusions (1.5 hour).

The study will consist of up to a 21-day screening period, a treatment period, a safety follow-up (SFU) visit conducted 30 (+7) days after the last dose of AMG 562, and a long-term follow-up (LTFU) period that will begin after the SFU visit is completed. Subjects will be followed for response evaluation at week 5, week 15, week 25 and at end of treatment if end of treatment is at week 35 or beyond (± 3 days). Subjects who

stopped response evaluations will be followed every 3 months (± 2 weeks) for survival follow-up. The total duration of the LTFU will be up to 2 years from the first dose of AMG 562.

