#### 9.7 Other Analyses

## 9.7.1 Analyses of Pharmacokinetic or Pharmacokinetic/Pharmacodynamic Endpoints

The PK analyses will be performed by CPMS group.

Serum concentrations of AMG 562 will be determined using a validated assay.

PK parameters will include, but are not limited to maximum observed concentration ( $C_{max}$ ), minimum observed concentration ( $C_{min}$ ) and area under the concentration-time curve over the dosing interval [AUC] and if feasible half-life ( $t_{1/2}$ ). Pharmacokinetic parameters will be estimated using standard non-compartmental approaches based on the PK analysis set and summarized by dose level using means, standard deviations, medians, minimums, and maximums.

Serum concentrations below the lower limit of quantification will be set to zero for the estimation of the pharmacokinetic parameters for each subject and for the calculation of the summary statistic for each time point. Actual dosing and sampling time will be used for all calculations. The reasons for excluding any sample from the analyses will be provided.

Individual concentration-time data will be summarized by dose level. Individual concentration-time data will also be tabulated and presented graphically. Summary statistics will be computed for each sampling time and parameter as appropriate.

Additional PK analyses, including but not limited to analysis of the relationship between AMG 562 dose and exposure parameters (AUC and  $C_{max}$ ) and dose proportionality assessments, may also be conducted.

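### Appendix I's symmetric ± 15 minute window permits the end-of-infusion PK sample before the infusion stops, which can bias observed Cmax low (worst case about 17–25% for one sample)

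*Protocol*

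**What the plan says.** - **Window.** The sampling scheme in Protocol Appendix I has a column headed "Suggested PK Draw Windows". It shows ± 15 minutes against the EOI sample on Days 8 and 15. On Days 1 and 22 the same tolerance appears to be one merged cell covering predose, EOI, 6 h and 12 h; this is inferred, because the table is broken in the available text.
- **Status of the window.** Protocol section 7.2, in its list of acceptable deviation windows, says "PK blood draws see Appendix I".
- **Footnotes.** Table 8 footnote r, and the matching footnotes to Tables 9, 10 and 11, say the EOI sample "should be collected as close as possible to the end of infusion of AMG 562". They ask for PK samples in general at the exact nominal time.
- **Infusion length.** Protocol section 2.4.1 refers to the starting dose "following a clinical IV infusion (1 hour) is predicted" to reach a given concentration. SAP section 3.1 gives 1.5 hours. The length column in Appendix I is blacked out.
- **Use of Cmax.** It is a secondary PK endpoint, estimated by non-compartmental methods (protocol section 10.5.3.1, SAP section 9.7.1). The SAP adds: "Actual dosing and sampling time will be used for all calculations". It has no rule for an EOI sample drawn before the infusion stopped.

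**The concern.** During a constant-rate infusion of a slowly cleared drug, concentration climbs almost linearly until the infusion stops. A sample 15 minutes before the stop is therefore systematically below the peak, yet inside the window. Against an infusion of 1 to 1.5 hours, 15 minutes is a sizeable fraction.

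Recording the actual time puts the sample in the right place on the time axis and so helps AUC. It does not restore the peak, because non-compartmental Cmax is the highest value observed. On Days 8 and 15 Appendix I has no other post-dose sample. Under step-up dosing, intermediate doses need only predose and EOI samples (Table 9 footnote r).

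At stake is the accuracy of observed Cmax by dose. The dose level review team (DLRT) sees PK with the other data when recommending doses. The first two planned cohorts have one subject each and later ones 3 to 4, so a single early draw can be a large part, or all, of a cohort's Cmax summary.

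**Working it through.** **1. The plan's own Cmax figure.** The documents state no figure for Cmax understatement. The one readable Cmax comparison is the exposure margin in Table 5, defined as monkey day-26 Cmax ÷ predicted human steady-state Cmax ÷ 17. Monkey Cmax at 5 µg/kg is 0.182 µg/mL = 182 ng/mL.
- With the printed 0.03 ng/mL at 0.1 µg: 182/0.03/17 = 357.
- With the less rounded value implied by the 0.3 µg row (0.1/3 = 0.0333 ng/mL): 182/0.0333/17 = 321.

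The stated 320 is therefore reproduced, within rounding. Its human input is a model prediction; no trial sample enters it.

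**2. Early draw, first dose.** Inputs: T = 1 h or 1.5 h, draw 0.25 h early, zero predose level. The linear approximation is 0.25/T; with disposition rate k the deficit is 1 − [1 − exp(−k(T − 0.25))]/[1 − exp(−kT)]. The late-draw deficit, 0.25 h after the stop, is 1 − exp(−0.25k). The documents give half-lives of 210 h (monkey) and about 384 h (predicted human terminal). The early distribution half-lives of 1 and 6 h are assumptions.

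| Half-life | Early, T = 1 h | Early, T = 1.5 h | Late (+15 min) |
|---|---|---|---|
| linear | 25.0% | 16.7% | – |
| 384 h | 25.0% | 16.7% | 0.05% |
| 210 h | 25.0% | 16.6% | 0.08% |
| 6 h (assumed) | 23.9% | 15.5% | 2.9% |
| 1 h (assumed) | 18.9% | 10.4% | 15.9% |

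**3. Repeat doses.** A carried-over level shrinks the relative error. As a stand-in for the trough, take the average concentration from Table 5 at 0.1 µg: 0.41/168 = 0.0024 ng/mL, which is 7–8% of Cmax (0.0333 or 0.03 ng/mL). The deficit is (1 − 0.08) × 25% ≈ 23% for 1 h and (1 − 0.08) × 16.7% ≈ 15% for 1.5 h.

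**4. Days 1 and 22, where a 6 h sample exists.** Observed Cmax cannot fall below the 6 h value. With one-exponential decline, that value relative to the peak is 2^(−(6 − T)/half-life).
- 384 h: 2^(−5/384) = 99.1% (1 h infusion), 2^(−4.5/384) = 99.2% (1.5 h). The loss is capped at about 1%.
- 48 h: 93.0% and 93.7%. The loss is capped at about 6–7%.
- 12 h: 74.9% and 77.1%, below the early-draw values of 75.5% and 83.9%. The 6 h sample gives no protection.

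The cap thus works only if decline is slow.

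**5. Typical rather than extreme.** If draws were uniform over the whole window (an assumption), half would be early with a mean loss of 12.5% or 8.3%. Averaged over all draws, that is about 6% (1 h) or 4% (1.5 h).

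**The case against.** The strongest reply is that the footnotes already tie the draw to the end of the infusion, and that the Appendix I window is only a suggestion: a clock tolerance around a nominal hour rather than leave to sample early. This stands in part. A draw 15 minutes early is the limit of tolerance, not the instruction. But section 7.2 makes Appendix I the acceptable deviation window, and closeness in the footnotes has no direction. A compliant early draw therefore remains possible.

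The 6 h sample is a fair objection to quoting 17–25% everywhere. It limits the loss on Days 1 and 22 if decline is slow, and does nothing on Days 8 and 15.

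A later draw is not free either. With fast early distribution it loses about 3–16%. At an assumed 1 h half-life with a 1.5 h infusion, the late edge loses more than the early edge (15.9% against 10.4%). That argues for a prompt draw, not for keeping the early tolerance.

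The use of Cmax is also limited. The dose-toxicity model is fitted to DLTs, no Cmax threshold governs a dose decision, and the dose-exposure and dose-proportionality analyses in SAP section 9.7.1 are optional. Infusion stop times (protocol section 6.2.1.1) and PK collection times are recorded, so early draws can be identified. Finally, the study was discontinued, with one subject ongoing at the primary snapshot (SAP sections 1 and 7.2), so a protocol edit can change few samples.

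**Conclusion.** The point holds as a minor, cheap improvement. The window admits EOI samples drawn on the rising part of the curve, and the error this causes in observed Cmax is always downward. The size is up to about 25% (1 h infusion) or 17% (1.5 h) for one first-dose sample at the early edge. It is about 23% or 15% with carry-over, and about 1–7% on Days 1 and 22 if decline is slow. Nothing in the documents suggests that draws cluster at the edge, so these are worst cases, not expected errors.

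The figures assume a constant infusion rate and the two infusion lengths printed outside the blacked-out fields. Those two passages need to be reconciled. For Days 1 and 22 the window itself is inferred.

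A reader might infer that the safety margin against the monkey data is overstated. If a margin were formed from an observed Cmax that was 25% or 16.7% low, it would be 1/0.75 = 1.33 or 1/0.833 = 1.20 times too high. The documents do not do this: Table 5 uses model-predicted human exposure, and no section recomputes a margin from trial samples. The supported consequence is a low bias and added variability in a secondary endpoint that reaches the DLRT among the PK data.

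**What to change.** **Protocol Appendix I:** replace the EOI window with 0 to +15 minutes after the actual infusion stop, drawn as promptly as possible. State the same direction in the footnotes to Tables 8 to 11 and in the laboratory manual.

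**SAP section 9.7.1:** add a sentence that EOI samples whose actual time precedes the recorded infusion stop are flagged, and that Cmax is summarised with and without them. Excluding them outright would discard scarce values in cohorts of 1 to 4 subjects.

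**Cost:** a change to one table entry with matching wording, and one SAP sentence; no extra samples or data. The narrower window means a few more draws will fall outside it, and a late draw can still miss some of the peak if early distribution is fast. Because the study stopped early, the protocol edit helps mainly any remaining dosing and later studies that reuse the scheme. The SAP sentence can be applied to the samples already collected.
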